11.11.3 Tumor Lysis Syndrome

Common Terminology Criteria for Adverse Events (CTCAE) version 5.0 classifies TLS in grade 3 (present), grade 4 (life threatening consequences; urgent intervention indicated) and grade 5 (death). Cairo and Bishop developed a system for defining and grading TLS based on Hande-Garrow classification of laboratory or clinical TLS (Coiffier et al, 2008). In this trial, the Cairo-Bishop classification will be used to define presence of TLS; ie, presence of laboratory TLS (see [Table 11-8](#)) and clinical TLS. Final event grade will be assigned according to CTCAE version 5.0.

Based on the Cairo and Bishop system, laboratory TLS is defined as any 2 or more abnormal serum values present within 3 days before or 7 days after initiation of treatment in the setting of adequate hydration (with or without alkalinization) and use of a hypouricemic agent ([Table 11-8](#)).

Table 11-8. Cairo-Bishop Definition of Laboratory Tumor Lysis Syndrome

Element	Value	Change from baseline
Uric acid	$\geq 476 \mu\text{mol/L}$ or 8 mg/dL	25% increase
Potassium	$\geq 6.0 \text{ mmol/L}$ or 6 mg/L	25% increase
Phosphorus	$\geq 2.1 \text{ mmol/L}$ for children or $\geq 1.45 \text{ mol/L}$ for adults	25% increase
Calcium	$\leq 1.75 \text{ mmol/L}$	25% decrease

Note: Two or more laboratory changes within 3 days before or 7 days after cytotoxic therapy will constitute laboratory tumor lysis syndrome.

Clinical TLS requires the presence of laboratory TLS in addition to 1 or more of the following significant complications: renal insufficiency, cardiac arrhythmias/sudden death, and seizures.

Approval Signatures

Document Name: Protocol Amendment tarlatamab 20230273 2

Document Description: Tarlatamab 20230273 PA1- development for a China only study

Document Number: CLIN-000332994

Approval Date: 06 Sep 2024

Type of Study Protocol: Amendment

Protocol Amendment No.: 2

Document Approvals	
Reason for Signing: Management	Name: [REDACTED] Date of Signature: 06-Sep-2024 15:25:09 GMT+0000

Amendment 1

Protocol Title: Phase 2a Study Evaluating the Efficacy, Safety, Tolerability, and Pharmacokinetics of Tarlatamab in Chinese Subjects with Advanced Small Cell Lung Cancer after Two or More Prior Lines of Treatment (DeLLphi-307)

Amgen Protocol Number: 20230273

Amendment Date: 15 May 2024

Rationale:

This protocol is mainly being amended to update the objectives and endpoints to include efficacy as a primary endpoint and pharmacokinetics (PK) as secondary endpoint along with safety and tolerability. Changes including, but not limited to, the following were incorporated into the protocol:

- Updated the phase throughout the protocol from a phase 1b to a phase 2a.
- Updated the protocol to replace mention of “preliminary anti-tumor activity” to “efficacy” throughout the protocol.
- Updated the objectives and endpoint sections to:
 - clarify that the primary objective was to evaluate efficacy of tarlatamab as assessed by objective response rate (ORR) based on blinded independent central review (BICR) per Response Evaluation Criteria in Solid Tumors Version 1.1 (RECIST 1.1).
 - Incorporate two new efficacy secondary endpoints to:
 - evaluate the efficacy of Tarlatamab as assessed by ORR based on investigator assessment per RECIST 1.1.
 - evaluate efficacy of Tarlatamab as assessed by duration of response (DOR), disease control (DC), and progression-free survival (PFS), based on BICR and investigator assessment per RECIST 1.1.
 - evaluate efficacy of Tarlatamab as assessed by overall survival (OS)

- include PK and immunogenicity as secondary endpoints
 - include estimand(s) for primary objective(s)
- Updated overall design section to clarify that Chinese subjects will include those with advanced small cell lung cancer (SCLC) who have progressed on or recurred following 1 platinum-based regimen as 1L therapy (including a PD-1/PD-[L]1) and at least 1 other prior line of therapy (re treatment with a platinum-based regimen is considered a second-line of therapy).
- Updated the number of Chinese subjects in this study from 15 to 30.
- Monitoring guidance for subjects has been updated from a minimum of 24 hours post-infusion to 6 to 8 hours for cycle 1 day 1 and cycle 1 day 8 throughout the protocol where applicable.
- Added a new section (Section 4.4) to capture details on the justification for monitoring.
- Updated Table 8-1 (Section 8.4.1) to align with Schedule of Activities (Section 1.3).
- Updated radiological imaging assessment section (Section 8.3.1) to clarify that scans will be submitted to a central imaging core laboratory for archival, response assessment by BICR including RECIST 1.1, and/or [REDACTED].
- Incorporated new BICR Section (Section 8.3.2).
- Updated antibody testing procedure (Section 8.7) to clarify that samples testing positive for binding antibodies will be evaluated for anti-tarlatamab neutralizing antibodies.
- Updated statistical consideration section (Section 9) to update the sample size determination, planned analyses, population for analysis, and exposure to investigational product language.
- Updated Appendix 3 (Section 11.3) to incorporate quality tolerance limit parameters (QTLs) language.

- General editorial changes, including administrative, abbreviations, typographical, and formatting corrections have been made throughout the protocol for clarification.

Amendment 2

Phase 2a Study Evaluating the Efficacy, Safety, Tolerability and Pharmacokinetics of Tarlatamab in Chinese Subjects with Advanced Small Cell Lung Cancer after Two or More Prior Lines of Treatment (DeLLphi-307)

Amgen Protocol Number AMG 757 20230273

NCT Number: NCT06502977

Amendment Date: 06 September 2024

Rationale:

This protocol has been amended to align with the United States Prescribing information for tarlatamab and other clarifications throughout the protocol. Changes including the following were incorporated into the protocol:

- Addition of the NCT number
- Addition of language regarding the accelerated approval of tarlatamab from the United States Food and Drug Administration
- Revision of the duration of the safety follow-up visit for alignment with the tarlatamab approved label
- Revision of disease progression language to specify that subjects will receive study treatment until blinded independent central review-confirmed disease progression per RECIST 1.1, death, withdrawal of consent, start of new anticancer therapy, unacceptable toxicity, or end of study as determined by the sponsor (whichever occurs first)
- Clarification of the New York Heart Association data collection
- Clarification of the timing of screening local laboratory assessments
- Clarification of the timing of laboratory assessments prior to cycle 1 day 1 dose
- Revision of inclusion criterion to clarify that extensive-stage small cell lung cancer could be enrolled
- Revision of contraception and lactation language to align the timing with the tarlatamab approved label
- Addition of dose modification guidance for hypersensitivity (allergic reactions)
- Safety language was updated when applicable to align with most recent guidance from Amgen safety and pharmacovigilance.
- Hepatotoxicity guidelines were updated to align with most recent guidance from Amgen safety
- Addition of End of Treatment section

ALT	alanine aminotransferase
AST	aspartate aminotransferase
ASTCT	American Society for Transplantation and Cellular Therapy
BICR	blinded independent central review
BMI	body mass index
BOR	best overall response
C1D1	cycle 1 day 1
CI	confidence interval
CR	complete response
CRF	case report form
CRS	cytokine release syndrome
CT	computed tomography
CTCAE	Common Terminology Criteria for Adverse Events
DC	disease control
DCO	data cut-off
DCR	disease control rate
DoDC	duration of disease control
DOR	duration of response
ECG	electrocardiogram
ECOG	Eastern Cooperative Oncology Group
eCRF	electronic case report form
GSO-DM	Global Study Operations-Data Management
ICANS	immune-effector cell associated neurotoxicity syndrome
IP	investigational product
IPD	Important protocol deviations
KM	Kaplan-Meier
LTFU	long-term follow-up
MedDRA	Medical Dictionary for Regulatory Activities
MG	milligram
MRI	magnetic resonance imaging
NCT	National Clinical Trials
NE	not evaluable
OR	objective response
ORR	objective response rate

OS	overall survival
PD	progressive disease
PFS	progression-free survival
PK	pharmacokinetic
PR	partial response
QTc	corrected QT interval
RECIST 1.1	Response Evaluation Criteria in Solid Tumors Version 1.1
SAP	statistical analysis plan
SCLC	small cell lung cancer
SD	stable disease
SFU	Safety follow-up
SOC	standard of care
T1	timepoint 1
T2	timepoint 2
TEAE	treatment-emergent adverse event
TLS	tumor lysis syndrome
TRAE	treatment-related adverse event
ULN	upper limit of normal
WHO	World Health Organization

1. Introduction

The purpose of this Statistical Analysis Plan (SAP) is to provide details of the statistical analyses that have been outlined within the protocol **amendment 2.0** for study 20230273, Tarlatamab (AMG 757) dated **06Sep2024**. The scope of this plan includes the primary analysis and the final analysis that are planned and will be executed by the Amgen Global Biostatistical Science department unless otherwise specified. Pharmacokinetic/Pharmacodynamic analyses will be provided by the Department of Clinical Pharmacology, Modeling and Simulation (CPMS).

2. Objectives, Endpoints/Estimands and Hypotheses

2.1 Objectives and Endpoints/Estimands

Objectives	Endpoints
Primary	

Evaluate efficacy of tarlatamab as assessed by objective response rate (ORR) based on blinded independent central review (BICR) per Response Evaluation Criteria in Solid Tumors version 1.1 (RECIST 1.1)	
ORR BICR, defined as proportion of subjects with best overall response (BOR) of complete response (CR) or partial response (PR)
Secondary	

Evaluate efficacy of Tarlatamab as assessed by duration of response (DOR), disease control (DC) and progression-free survival (PFS) based on BICR per RECIST 1.1	
DOR, defined as time from the first documentation of objective response (OR) until the first documentation of disease progression or death due to any cause, whichever occurs first. Only subjects who have achieved OR will be evaluated for DORDC, defined as a BOR of CR or PR or stable disease (SD)Duration of DC, defined as time from the first documentation of CR or PR or SD until the first documentation of disease progression or death due to any cause, whichever occurs first. Only subjects who have achieved CR or PR or SD will be evaluated for duration of DCPFS, defined as time from enrolment until disease progression or death from any cause, whichever occurs first. Progression will be based on RECIST 1.1.

Evaluate efficacy of Tarlatamab as assessed by ORR, DOR, DC and PFS based on investigator assessment per RECIST 1.1	
ORR (Investigator)DOR (Investigator)DC (Investigator)Duration of DC (Investigator)PFS (Investigator)

Evaluate efficacy of Tarlatamab as assessed by overall survival (OS)	
OS, defined as time from enrolment until death from any cause

Evaluate safety and tolerability	
Incidence of treatment-emergent adverse events

Characterize the pharmacokinetics of tarlatamab	
Serum concentration of tarlatamab

Evaluate the immunogenicity of tarlatamab	
Incidence of anti-tarlatamab antibody formation

Estimand(s) for Primary Objective(s)

ORR by BICR per RECIST 1.1 in Chinese subjects with advanced SCLC who have progressed on or recurred following 1 platinum-based regimen as 1L therapy (including a PD-1/ PD-[L]1) and at least 1 other prior line of therapy (re-treatment with a platinum based regimen is considered a second-line of therapy) prior to start of new cancer therapy (while-on-treatment strategy).

Estimand(s) for Key Secondary Objective(s)

Not applicable.

2.2 Hypotheses and/or Estimations

No statistical hypotheses will be tested.

3. Study Overview

3.1 Study Design

This is a phase 2a, multicenter, single arm, open-label study in Chinese subjects with advanced SCLC who have progressed on or recurred following 1 platinum-based regimen as 1L therapy (including a PD-1/PD-[L]1) and at least 1 other prior line of therapy (re-treatment with a platinum-based regimen is considered a second line of therapy). The study consists of a 21-day screening period, a treatment period, a safety follow-up (SFU) period, and a long-term follow-up (LTFU) period.

A SFU visit will occur 60 (+ 5) days after the last dose of tarlatamab regardless of initiation of subsequent anticancer therapy within that period. After the SFU visit,

subjects will be followed in LTFU for survival every 12 weeks (+/-14 days) for up to 1 year after the **last** subject's last dose of tarlatamab or 5 years from the first subject enrolled, whichever occurs first.

3.2 Sample Size

Approximately 30 subjects will be enrolled in the study. With 30 subjects enrolled at the target dose, the probability that the observed ORR will be greater than **different thresholds are presented in Table 3.2-1.**

Table 3.2-1. Probabilities of Observed ORR Greater Than Thresholds With Sample Size of 30

True ORR	Probability of Observed ORR > 25 %	Probability of Observed ORR > 30%
0.35	88%	64%
0.4	96%	82%

With 30 subjects, there is a 79% to 96% probability of observing at least 1 adverse event if the true event rate is 5% to 10%.

3.3 Adaptive Design

Not applicable.

4. Covariates and Subgroups

4.1 Planned Covariates

The relationship between relevant covariates and efficacy endpoints may be explored if appropriate. The following baseline covariates may be summarized as appropriate.

- Race
- Sex
- Age at enrollment in years
- ECOG performance status at baseline
- Prior lines of therapy
- Metastatic
- Sum of diameters of target lesions at baseline based on investigator assessment (mm)

4.2 Subgroups

Not applicable.

5. Definitions

5.1 General Definitions

Baseline

For any variable, unless otherwise specified, baseline is the last non-missing assessment taken prior to the first administration of tarlatamab. Where baseline measurements are taken on the same day as the tarlatamab administration and no time is present, it is assumed that these measurements are taken prior to tarlatamab administration.

Change from Baseline

Change from baseline = post-baseline value – baseline value.

Percent Change from Baseline

Percent change from baseline = $100 * (\text{post-baseline value} - \text{baseline value}) / \text{baseline Value}$

Body Mass Index (BMI)

$\text{BMI (kg/m}^2\text{)} = \text{weight (kg)} / [\text{height (cm)} / 100]^2$

Investigational Product (IP)

Investigational product refers to tarlatamab.

Study Day

Study day = (date - date of study day 1) + x; where

x = 1 if date is after study day 1;

x = 0 if date is before study day 1.

Study Day 1

Study day 1 is defined as the date of the first dose of tarlatamab administration to the Subject.

Treatment Duration

Treatment duration (weeks) = (last dose date – first dose date + 1) / 7.

Relative Dose Intensity

Relative dose intensity (%) = $100 * (\text{Actual cumulative dose} / \text{Planned cumulative dose})$;

Actual cumulative dose = sum of received doses.

Planned cumulative dose = planned dose accumulated over the actual treatment duration,

i.e., $10 \text{ mg} \times (\text{number of records in exposure dataset} - 1) + 1 \text{ mg}$; 1 mg is the step dose on C1D1.

Actual and planned cumulative dose up to the study visit are considered.

Last Known Alive Date

Last known alive date is the latest date of the following dates before death date. Other Case Report Form (CRF) data may be explored to get the last known alive date. Last known alive date should be imputed the first day of the month for the partial date when the month and year are available, but day is missing.

- Date of consent signed, and date of consent withdrawn from additional consents/withdrawals of consent form
- Date of Enrollment date on Subject Enrollment CRF
- Date First Taken, Date Last Taken on Concomitant Medications CRF
- Date Performed on MUGA/ECOG Performance Status, Vital Signs, Echocardiogram, Electrocardiogram, Surgical Procedures, Procedure CRFs
- Admission Date, Discharge Date on Hospitalizations CRF, Date of Examination on Physical Measurement CRF
- Date Collected on Reproductive Status and Pregnancy Test (Local Lab), Chemistry (Local Lab), Hematology (Local Lab), Coagulation (Local Lab) CRFs, Urinalysis (Local Lab) and in central lab data
- Start Date, Stop Date on Product Administration CRF
- Start Date, Stop Date on Other Protocol Required Therapy CRF
- Date Started and Date Ended on Events CRF for non-fatal events
- Tumor response and NYHA Classification date
- Target/non-target assessment date
- CRS Symptoms and ICANS date

- End of study, end of safety follow-up and end of administration date where end reason is not death or lost to follow-up
- Start date, Stop date on On-Study Radiotherapy, Anti-Cancer Therapies (Subsequent) CRF
- Subject Status Date if status is Alive on Survival Status CRF
- Assessment Date of CT or MRI
- Date of Liver biopsy
- Neurological Evaluation date
- Date of Clinical Outcome Assessments
- If death happened, then last known alive date is death date minus 1.
- Date of Anti-body sample
- Date of PK sample
- Date/Time of Tumor Measurement
- Date/Time of Tumor Identification
- Date/Time of Response Assessment

End of IP Administration

End of IP administration for each subject is defined as the date the decision was made to end IP as recorded on the End of Product Administration eCRF page.

End of Study Date (End of Trial)

The end of study date for the entire study is defined as the date when the last subject across all sites is assessed or receives an intervention for evaluation in the study (ie, last subject last visit) including any additional parts in the study (eg, LTFU, antibody testing), as applicable.

End of Study (Individual Subject)

End of study for each subject is defined as the date the subject last completed a protocol specified procedure. The date will be recorded on the End of Study eCRF page.

Safety Follow-up (SFU)

Upon permanent discontinuation from the study treatment for any reason, a safety follow up visit will be performed approximately 60 (+ 5) days after the end of the last dose of tarlatamab, regardless of initiation of subsequent anticancer therapy within that period.

Long Term Follow-up (LTFU)

Following the SFU visit (60 [+ 5] days), subjects will enter the LTFU period for clinical evaluation of disease status and survival. Subjects will be followed via telephone, clinic visit, or chart review to assess for survival and/or the commencement of subsequent cancer therapy every 12 weeks (\pm 14 days) from the SFU visit or last imaging visit, whichever is later, for up to 1 year after the last subject's last dose of tarlatamab or 5 years from first subject enrolled, whichever occurs first.

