4.1 Overall Design

This is a phase 2a, multicenter, single arm, open-label study in Chinese subjects with advanced SCLC who have progressed on or recurred following 1 platinum-based regimen as 1L therapy (including a PD-1/PD-[L]1) and at least 1 other prior line of therapy (re-treatment with a platinum-based regimen is considered a second-line of therapy).

Approximately 30 Chinese subjects are planned to be enrolled in the study.

The study consists of a 21-day screening period, a treatment period, a safety follow-up (SFU) period, and a long-term follow-up (LTFU) period.

Study treatment will be administered as follows:

- Tarlatamab will be administered as a 60-minute (\pm 10 minutes) intravenous (IV) infusion with 1 mg step dose on cycle 1 day 1 (C1D1) followed by a 10 mg target dose on cycle 1 day 8 (C1D8), and cycle 1 day 15 (C1D15) in a 28-day cycle. Subsequent doses (10 mg) will be administered every 2 weeks (Q2W) (ie, cycle 2+ day 1/day 15 dosing) in a 28-day cycle.
- Monitoring during cycle 1:
 - Monitoring – cycle 1: Monitoring required for 6 to 8 hours post-infusion at C1D1 and C1D8.
 - Cohabitant (caregiver) support for 24 hours post-infusion and the ability to stay within 1 hour of a hospital for 24 hours is required.
 - Counseling the subject and caregiver on signs and symptoms of CRS, and ICANS by a health care provider is required prior to discharge.
 - Subjects return to site on cycle 1 day 2 (C1D2) and cycle 1 day 9 (C1D9) for vital signs and physical examination.
 - At subsequent visits, additional monitoring may be required post-infusion. Refer to Section 6.1.1 (Table 6-1).
- Pre- and Post-infusion medication requirements:

- Dexamethasone: 8 mg IV (or equivalent dose of other corticosteroids) will be administered within 1 hour prior to tarlatamab infusion on C1D1 and C1D8.
- Intravenous Hydration: 1 L normal saline over 2 to 4 hours following tarlatamab administration on C1D1 and C1D8.

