^d CRS grade is determined by the more severe event: hypotension or hypoxia not attributable to any other cause. For example, a subject with temperature of 39.5°C , hypotension requiring 1 vasopressor, and hypoxia requiring low-flow nasal cannula is classified as grade 3 CRS.

^e Low-flow nasal cannula is defined as oxygen delivered at ≤ 6 L/minute. Low-flow also includes blow-by oxygen delivery, sometimes used in pediatrics. High-flow nasal cannula is defined as oxygen delivered at > 6 L/minute.

^f For neutropenia adverse events grade ≤ 2 , please follow institutional guidelines for management.

For all other treatment interruptions or delays, restart tarlatamab in accordance with the following guidelines in [Table 6-3](#):

Table 6-3. Step dose Rechallenge Requirement After Tarlatamab Delay

Last Dose Administered	Duration of Delay from the Last Dose Administered	Action
Step dose (1 mg)	≤ 14 days	Proceed with tarlatamab 10 mg target dose and then continue treatment Q2W.
	> 14 days	Repeat tarlatamab 1 mg step dose per cycle 1 guidelines, including pre-medication and monitoring requirements (refer to Table 6-1).
First target dose (10 mg)	≤ 21 days	Proceed with tarlatamab 10 mg target dose and then continue treatment Q2W.
	> 21 days	Repeat tarlatamab 1 mg step dose schedule per cycle 1 guidelines, including pre-medication and monitoring requirements (refer to).
Any subsequent target dose (10 mg)	≤ 28 days	Proceed with tarlatamab 10 mg target dose and then continue treatment Q2W.
	> 28 days	Repeat tarlatamab 1 mg step dose per cycle 1 guidelines, including pre-medication and monitoring requirements (refer to Table 6-1).

Q2W = every 2 weeks.

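### The relative dose intensity formula counts exposure records instead of scheduled doses, so delays without a repeat step dose, and isolated omissions without a 0 mg record, do not lower it

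*SAP*

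**What the plan says.** SAP 5.1 defines RDI as 100 times actual over planned cumulative dose. The numerator is plain: "Actual cumulative dose = sum of received doses". The denominator is described in words as "planned dose accumulated over the actual treatment duration", and a formula is then offered as its equivalent: 10 mg × ("number of records in exposure dataset" − 1) + 1 mg, with the note that "1 mg is the step dose on C1D1". Both doses are taken up to the study visit. The same section defines "Treatment duration (weeks) = (last dose date – first dose date + 1) / 7", but the RDI formula does not use it. SAP 9.6.3 and Protocol 9.4.2.3.7 both list RDI among the exposure summaries.

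Protocol 4.1 sets the schedule: 1 mg on day 1, 10 mg on days 8 and 15, then 10 mg every 2 weeks from cycle 2 day 1 (day 29). Protocol 8.1.2 ties all later doses to the day 1 date, with windows of ±1 day for days 8 and 15 and ±3 days from cycle 2. Table 6-2 answers neurologic events, CRS, tumor lysis syndrome and neutropenia by delay or discontinuation and has no reduced-dose step.

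Table 6-3 lets dosing continue at 10 mg if the gap is at most 14, 21 or 28 days after the step dose, the first target dose or a later target dose. Beyond those limits it requires a restart, for example: "Repeat tarlatamab 1 mg step dose per cycle 1 guidelines, including pre-medication and monitoring requirements".

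Protocol 6.6 has each administered dose recorded. Neither document says whether the exposure dataset holds a 0 mg record for an omitted dose.

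**The concern.** The words and the formula describe different quantities. The words give a schedule-based denominator, which grows with the calendar. The formula gives a record-based one, which grows only when a record is added. They agree only if every dose scheduled up to the last one has a record. A programmer will code the formula.

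RDI is the exposure summary meant to show how much of the intended dose was delivered. Here dose is lost to toxicity mainly through delayed and omitted infusions, and the record count is least able to register those. Reported RDI could then look close to complete in subjects who received well under the scheduled dose.

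**Working it through.** The SAP gives a formula but no RDI value, so there is no stated figure to reproduce. The dosing histories below are illustrative and not trial data.

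**Definitions.** Let A be the total mg received, n the number of exposure records and L the day of the last dose.

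- SAP formula: RDI = 100 × A / [10(n − 1) + 1].
- SAP words: RDI = 100 × A / P(L), where P(L) = 1 + 10 × (number of target days 8, 15, 29, 43, … up to L). This gives P(141) = 1 + 10×11 = 111 mg, P(155) = 1 + 10×12 = 121 mg and P(169) = 1 + 10×13 = 131 mg.

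A full target dose adds 10 to both A and 10(n − 1) + 1, whenever it is given. So any history of one 1 mg dose followed by full 10 mg doses, with records only for doses given, scores exactly 100% by the formula.

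**Results, with records only for doses given**

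| History | A (mg) | n | Formula | Schedule |
|---|---|---|---|---|
| Full dosing to day 155 | 121 | 13 | 121/121 = 100% | 121/121 = 100% |
| Days 1, 8, 15, then every 21 days to day 141 | 81 | 9 | 81/81 = 100% | 81/111 = 73.0% |
| Days 1, 8, 15, then every 28 days to day 155 | 71 | 8 | 71/71 = 100% | 71/121 = 58.7% |
| Two isolated omissions, last dose day 169 | 111 | 12 | 111/111 = 100% | 111/131 = 85% |
| Four isolated omissions, last dose day 169 | 91 | 10 | 91/91 = 100% | 91/131 = 69% |

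No gap in the 21-day and 28-day rows exceeds the Table 6-3 limits, so no repeat step dose arises. The omission rows assume nominal visit days. One omitted two-weekly dose then leaves a 28-day gap, which is still within the limit.

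**Where the formula does move**

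- *0 mg records.* If each of the four omissions has a 0 mg record, n = 14 and the formula gives 91/131 = 69%, the same as the schedule.
- *Partial infusion.* One half dose in 13 records gives 116/121 = 95.9% by both.
- *Repeat step dose, short course.* 1, 10, 1 and 10 mg on days 1, 8, 30 and 37 gives 22/31 = 71% by the formula. The schedule to day 37 also plans 1 + 10×3 = 31 mg, so it too gives 71%. With the restart on day 44 and the last dose on day 51, the schedule gives 22/41 = 54%.
- *Consecutive omissions with a restart.* Doses on days 57 to 99 are missed (four doses). Dosing resumes with 1 mg on day 113, then 10 mg on days 120, 127, 141, 155 and 169. A = 41 + 51 = 92 mg and n = 11. The formula gives 92/101 = 91%; the schedule gives 92/131 = 70%.

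**The case against.** The strongest reply is that the documents do not describe the exposure dataset. If every scheduled slot that passes without an infusion receives a 0 mg record, the record count becomes a schedule count and the discrepancy for omitted doses disappears. This stands as a condition. The recording of administered doses in Protocol 6.6 makes such records unlikely but does not rule them out. For delays, they would help only if every calendar slot passed over also received a record, and no rule requires that.

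A reader might go further and infer that RDI is about 100% by construction, however many doses are held. The documents do not support that. Partial infusions lower the numerator, and Table 6-2 creates them when an infusion stopped for grade 3 hypersensitivity is not resumed. Long gaps bring in a repeat 1 mg dose that is scored against 10 mg, as in the 91% example.

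A reader might also infer that repeat step doses lower RDI artificially. That depends on the reference chosen. Against the original schedule the subject did receive less, and a schedule-based denominator falls as far or further. The penalty is artificial only if the planned dose is taken to be what Table 6-3 requires at that visit, and the SAP does not say which is meant. Nor do the documents show that a paused and restarted infusion would be split into two records.

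Finally, RDI is not an endpoint and no hypothesis is tested. SAP 9.6.3 also reports number of doses, cumulative dose, treatment duration and dose modifications with reasons, and SAP 9.6.2 reports adverse events leading to interruption or withdrawal. Held doses therefore remain visible elsewhere. This limits the consequence but does not make the formula match its definition.

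**Conclusion.** The point holds in a limited form. SAP 5.1 contradicts itself, and the version that would be programmed cannot register delays that stay within the Table 6-3 limits. It also misses isolated omitted doses if these have no record. In the examples the overstatement is 27 percentage points for 21-day spacing (100 − 73.0), 41 for 28-day spacing (100 − 58.7) and 31 for four isolated omissions through day 169 (100 − 69).

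These sizes rest on assumed dosing histories at nominal days, on there being no 0 mg records and, in these three examples, on no restart being triggered. How often such histories will occur cannot be judged from the documents. The claims that RDI is near 100% by construction and that repeat step doses depress it artificially are not part of the conclusion. The effect is confined to a descriptive exposure summary; the ORR result does not depend on it.

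**What to change.** In SAP 5.1, replace the record count with the dose scheduled by the protocol from first dose through last dose date: 1 mg on day 1, plus 10 mg for each target dose due on days 8 and 15 and every 14 days from day 29. Keep the actual dose as the sum received.

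Count a scheduled dose as due if its visit window (±1 day in cycle 1, ±3 days later) has opened by the last dose date. Without this rule, a fully dosed subject whose last infusion falls on day 168 instead of day 169 would score 131/121 = 108%. With it, the day 169 dose is due from day 166 and the result is 131/131 = 100%.

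State whether a repeat 1 mg step dose under Table 6-3 counts in the planned dose as 1 mg or as the originally scheduled dose, because the calendar denominator does not settle this.

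The cost is one definition and a small program change. Reported RDI will be lower for subjects with delayed or unrecorded omitted doses, and unchanged for those dosed on schedule. Because the calculation stops at the last dose date, as the SAP's treatment duration does, doses held after the final infusion still do not count.
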